10.1 Sample Size

The recommended study size is 50 subjects: 25 in the treatment arm (Slit Stent II) and 25 in the control arm (BIKA for DCR). The sample size recommendation is based on two factors.

- It provides reasonable accuracy for estimates of proportions, means, and differences of proportions and of means. For categorical variables, the maximum half width of a 95% Wilson confidence interval for a single proportion is 0.18 (for $n=25$) and for a difference of two proportions is 0.27 ($n_1=n_2=25$). For continuous variables, the margin of error for a Welch t-interval for a mean is 0.41 standard deviations, and for a difference of two means it is 0.57 standard deviations. For example, if the standard deviation of the GBI score is 25 points, the margin of error for the confidence interval for the difference of treatment group GBI means is 14 points.
- It provides excellent power to show the new variation is non-inferior to the common lacrimal stent as measured by the GBI: Based on previous studies of lacrimal stents [11, 41-47] that assessed GBI, we estimate the standard deviation is about 25 points on the GBI scale and we set a non-inferiority boundary of $\delta = 20$ points ($20/25 = 0.80$, a 'large' effect in Cohen's taxonomy). If in fact the devices are equivalent (i.e., they have equal mean GBI scores, $\mu_{SSII} = \mu_{BIKA}$), then we have 87% power to demonstrate non-inferiority based on a single GBI measurement. Using all repeated observations would increase power even against a tighter non-inferiority boundary.

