10.0 DATA ANALYSIS AND STATISTICAL CONSIDERATIONS

A detailed statistical analysis plan (SAP) will be developed for analysis of all data for this study. Required analyses and target endpoints that will be included in this SAP are summarized below. The methods by which each of these analyses is performed will be included in the SAP. The required analyses and target endpoints for the Slit Stent II include, but are not limited to, those listed below. If there are any discrepancies between the statistical analyses described in the SAP versus this protocol, the SAP will prevail. Tabulation of summary statistics, graphical presentations, and statistical analyses will be performed using SAS® and/or R software. All subjects who are enrolled in this study will be included in the safety analysis. All testing and confidence intervals will use a two-sided significance level of 5%.

Specific analyses for the six listed objectives are very similar to one another. Data will be summarized by treatment group (Slit Stent II or BIKA for DCR): counts and percentages for categorical variables, means and standard deviations for continuous variables. Additionally, 95% confidence intervals will be provided for each treatment group and for the difference between treatment groups. The confidence intervals for differences are keys to exhibiting the similarity between the Slit Stent II and the existing BIKA stent.

As this is a randomized experiment, control for pre-treatment variables is not necessary. However, a sensitivity analysis controlling for the baseline measurement of the outcome variable will be conducted. For example, post-surgery Lac-Q will be regressed on treatment and pre-surgery Lac-Q. If pre- and post-surgery measures are highly correlated, the confidence interval for the treatment effect will be narrower (more precise). If measurements are made at multiple post-surgery time-points, (generalized) linear mixed models will be used to estimate an overall (fixed) treatment effect while accounting for any correlation between measurements on the same person (random intercept).

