10.5.3. Lac-Q Questionnaire (Appendix B)

This study does not aim to assess the effectiveness of the DCR procedure, which is a well-established surgical procedure for the treatment of epiphora secondary to nasolacrimal duct obstruction. Furthermore, the study does not aim to assess the effectiveness of using a silicone lacrimal stent as part of a lacrimal procedure. Rather, the primary goal of this study is to assess patient tolerance of the Slit Stent II, which introduces novel cuts into the traditional stent that allow for intraluminal tear drainage. The secondary goal of the study is to confirm that the Slit Stent II functions like any other silicone lacrimal stent as an adjunct to a lacrimal procedure. The effectiveness of the procedure in relieving the tearing symptoms and associated social isolation will be assessed at the pre-op visit and at each post-op visit. Scoring will follow the standard protocol (**Appendix B**). The Lac-Q questionnaire will always be given first among the questionnaires.

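### A pass at the 20-point GBI margin excludes only a deficit that the plan itself calls large, so it does not by itself show that the two stents are similar

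*Combined protocol and SAP*

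**What the plan says.** Section 10.1 rests the sample size on two things: the precision of estimates, and power for non-inferiority on the GBI. For the second it says "we estimate the standard deviation is about 25 points on the GBI scale", citing earlier studies for that figure, and sets the boundary at 20 points. The only remark on the size of the boundary is that 20/25 = 0.80 is "a 'large' effect in Cohen's taxonomy". On the assumption that "they have equal mean GBI scores", it states that "we have 87% power to demonstrate non-inferiority based on a single GBI measurement" and calls this power excellent. It adds that repeated observations would help against a tighter boundary, but names no value.

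Two other sections say what the comparison is meant to show. Section 10.0: "The confidence intervals for differences are keys to exhibiting the similarity between the Slit Stent II and the existing BIKA stent". Section 10.5.3: "The secondary goal of the study is to confirm that the Slit Stent II functions like any other silicone lacrimal stent". Neither gives a numerical limit for similarity. Section 10.5.2, on the GBI analysis, contains no non-inferiority test or decision rule. Section 10.0 announces a detailed SAP that would prevail over the protocol; no other margin appears in the document at hand.

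**The concern.** A non-inferiority margin is the largest loss one is prepared to disregard. A loss described as large is a poor candidate for that role unless something else supports it, and nothing else is offered: no minimally important difference, no control-arm mean, no share of benefit to be kept.

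The GBI makes this matter more. It scores change since surgery, and an answer of no change on every item gives 0 (Appendix A), so the control mean is itself the benefit.

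At stake is the wording of the result. As the plan stands, a lower limit just above -20 could be reported as non-inferior, and a reader of Sections 10.0 and 10.5.3 could take that as confirmation that the stents are alike.

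**Working it through.** **Inputs.** Margin 20, SD 25, 25 per arm, true difference 0 and stated power 87% (Section 10.1). Two-sided 5% level for all tests and intervals (Section 10.0). GBI total = (mean item response - 3) x 50 over 18 items (Appendix A).

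**The plan's own figures.**
- SE of the difference = 25 x sqrt(2/25) = 7.07.
- 95% half-width = t(48, 0.975) x SE = 2.011 x 7.07 = 14.2 points, or 0.57 SD. This matches the stated 14 points and 0.57 SD.
- Power uses the noncentral t with 48 df and noncentrality 20/7.07 = 2.83. At one-sided 5% it is 87.4%, which reproduces the stated 87%. At one-sided 2.5%, which corresponds to the two-sided 5% rule of Section 10.0, it is 79.1%.

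**What a pass requires.** The lower 95% limit exceeds -20 when the observed difference exceeds -20 + 14.2 = -5.8 (observed SD taken as 25). For example, an observed -5.7 gives an interval of about -19.9 to +8.5 and passes. On the 90% interval that underlies 87% power, the threshold is -8.1.

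**Chance of passing at margin 20 when Slit Stent II is truly worse by d.** Noncentrality (20 - d)/7.07:

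| True deficit d | One-sided 2.5% | One-sided 5% |
|---|---|---|
| 5 | 55% | 67% |
| 10 | 28% | 40% |
| 12.5 | 18% | 27% |
| 15 | 10% | 17% |

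**Power at equal means for other margins**, single measurement. Margins below 20 are illustrations, not taken from the plan:

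| Margin | In SD | One-sided 2.5% | One-sided 5% |
|---|---|---|---|
| 20 | 0.80 | 79% | 87% |
| 15 | 0.60 | 55% | 67% |
| 12.5 | 0.50 | 41% | 54% |
| 10 | 0.40 | 28% | 40% |

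**Repeated measurements.** Averaging k visits with within-person correlation r multiplies the variance by (1 + (k - 1)r)/k. For an assumed 2 to 3 visits and r from 0.3 to 0.9, power at one-sided 2.5% is 81% to 97% at margin 20, 43% to 66% at 12.5 and 30% to 48% at 10.

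**Size on the scale.** 20/50 = 0.4 of a response step on every item, or 0.4 x 18 = 7.2 steps in total.

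**Share of benefit.** No control mean is given. For assumed means of 20, 30 and 40, the margin is 20/20 = 100%, 20/30 = 67% and 20/40 = 50% of the benefit.

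**The case against.** The strongest reply is that the documents never say a non-inferior verdict proves similarity. That is right. Section 10.0 attaches similarity to the confidence intervals for differences, across all six objectives. Section 10.5.3 states a secondary goal under the Lac-Q heading and mentions neither the GBI nor the margin. A reader might infer that both sections draw their conclusions from the 20-point test, but the text does not make that link. What remains is that no other limit is offered, so an interval of about 14 points either side could be called similar on judgement alone.

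Further points stand in the plan's favour:
- Non-inferiority is not the only basis for the sample size. The precision argument needs no margin, and readers will see the interval.
- The Cohen label describes the margin in a parenthesis. The plan does not say that 20 was chosen because it is large. The fair criticism is that no other support is given.
- A pass still needs an observed deficit below 5.8 points, and a true 20-point deficit would pass only 2.5% of the time.
- The stated primary goal is patient tolerance. Sections 9.3.2 and 10.5.3 disclaim any assessment of DCR efficacy.
- Repeated measurements would add power. The gain at margins of 12.5 or below is modest, and the plan names no tighter margin.

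**Conclusion.** The point holds as one about justification and reporting, and it should be fixed. The plan's only margin lacks a clinical or preserved-benefit rationale. At SD 25 and 25 per arm, a pass is compatible with true deficits well short of trivial: 28% of trials with a 10-point deficit would pass, and 10% with a 15-point deficit. The description of the power as excellent belongs to the 20-point margin alone. These figures assume a single measurement, equal SDs, complete data and the two-sided 5% rule of Section 10.0.

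It is tempting to go further and say that the margin lets the new stent forfeit most or all of the benefit of surgery. The documents do not support that. The answer depends on a control mean they do not report: at an assumed mean of 40 the margin is half the benefit, and at 20 it is all of it. Nor do they show that 20 points is the wrong margin, only that its choice is unexplained.

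**What to change.** 1. In Sections 10.0, 10.1 and 10.5.3, state that a lower 95% limit above -20 will be reported, together with its interval, only as excluding a mean deficit of 20 GBI points or more. It will not be reported as similarity or as showing that Slit Stent II works as the standard stent does.
2. In Section 10.1, remove the Cohen label as support for the margin.
3. In the same section, limit the power claim to the 20-point margin and give the figures for a single measurement at two-sided 5%: 79% at 20, 55% at 15, 41% at 12.5 and 28% at 10.

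Keep n = 50. A tighter margin would need GBI means or an important difference from outside this document. That is for the sponsor to justify, and this point does not require it. The changes should be made before any comparison by treatment group is seen.

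The cost is protocol and SAP wording and a less favourable claim. No patients, visits or data are added.

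### The 87% non-inferiority power needs a one-sided 5% test; at the plan's own two-sided 5% level the power is 79%

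*Combined protocol and SAP*

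**What the plan says.** Section 10.0 sets one level for the whole analysis: "All testing and confidence intervals will use a two-sided significance level of 5" per cent. It adds that "95% confidence intervals will be provided for each treatment group and for the difference between treatment groups", and it treats the intervals for the differences as the main evidence that the two stents are alike.

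Section 10.1 gives two reasons for 25 patients per arm. The first is precision: margins of error of 0.41 SD for a mean, 0.57 SD for a difference of means, and 14 GBI points for the difference when the SD is 25. The second is power for non-inferiority on the GBI. There, "we estimate the standard deviation is about 25 points on the GBI scale", the margin is 20 points, the true means are taken as equal, and "then we have 87% power to demonstrate non-inferiority based on a single GBI measurement". The section calls this power excellent. It gives no significance level or sidedness for the non-inferiority test, and no allowance for loss of patients.

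**The concern.** A two-sided 5% level puts 2.5% in the tail that decides non-inferiority. Under the rule in section 10.0, the new stent is non-inferior when the lower limit of the 95% interval for the GBI difference (Slit Stent II minus BIKA) is above -20. The power figure should refer to that test, and 87% looks too high for it.

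Two things are at stake. This is the only power statement in the plan, and it supports the sample size. The mismatch also leaves the decision rule open: a result can be non-inferior by a 90% interval and not by a 95% interval. The choice between them must be fixed before the data are seen.

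**Working it through.** **Inputs.** From section 10.1: n = 25 per arm, SD = 25, margin = 20, true difference = 0, one GBI measurement. From section 10.0: two-sided 5%, so 0.025 in the deciding tail.

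**Formulas.** Standard error of the difference: SE = 25 × √(2/25) = 7.071. Noncentrality: λ = 20 / 7.071 = 2.828. Degrees of freedom: 2 × 25 − 2 = 48. Power = 1 − F(t₁₋α,₄₈; 48, λ), where F is the noncentral t distribution function and α is the one-sided level. The normal approximation is Φ(λ − z₁₋α).

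**Reproducing the stated 87%, then applying the plan's level.**

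| One-sided α | Interval | Noncentral t | Welch simulation (200,000 runs) | Normal approximation |
|---|---|---|---|---|
| 0.05 | 90% | 87.4% | 87.4% | Φ(2.828 − 1.645) = 88.2% |
| 0.025 (section 10.0) | 95% | **79.2%** | 79.3% | Φ(2.828 − 1.960) = 80.7% |

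The stated figure is a correct calculation for a one-sided 5% test. Other standard variants do not give it. One-sided 10% gives 93.6% (t). Two one-sided equivalence tests give 76.3% (5% each) or 61.5% (2.5% each), both by normal approximation.

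**Level used in the other half of section 10.1.** With t₀.₉₇₅,₄₈, the margin of error for the difference is 0.569 SD, or 14.2 points; with t₀.₉₇₅,₂₄, that for one mean is 0.413 SD. These match the stated 0.57 SD, 14 points and 0.41 SD. A 90% interval would have a margin of error of 11.9 points. So the precision figures use the 95% level and the power figure the 90% level, within one section.

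**Size of the ambiguous zone.** At SD 25 the two lower limits differ by 14.2 − 11.9, about 2.4 points before rounding (14.22 − 11.86). If -20 falls in that gap, the result passes under the rule implied by 87% and fails under section 10.0.

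**What would give 87% at the plan's level.** Any one of these, with the other inputs held: 31 per arm (87.3%), a margin of about 22.3 points, or an SD of about 22.4. By the t method, 80% is first exceeded at 26 per arm (80.8%).

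**Effect of loss.** The plan gives no dropout rate, so these are assumptions, at one-sided 0.025:

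| Evaluable per arm | Loss from 25 | Power |
|---|---|---|
| 24 | 4% | 77.4% |
| 22 | 12% | 73.6% |
| 20 | 20% | 69.3% |

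**The case against.** Several points can be made for the plan.

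- **The number is not miscalculated.** It is right for a one-sided 5% test, and the authors may have meant that. This is fair: section 10.1 does not state the level, so the level behind 87% is inferred. But section 10.0 covers all testing and makes no exception, so the two statements cannot both stand.
- **No explicit decision rule is written.** Section 10.5.2 plans only a 95% interval for the mean GBI score. Reading non-inferiority from the 95% interval for the difference is an inference. It is the natural one, because section 10.0 makes that interval the main comparison.
- **A later detailed SAP may set the level.** Section 10.0 says the SAP prevails over the protocol. That could settle the test, but it would not correct the figure in section 10.1.
- **Repeated measures help.** Section 10.1 says "Using all repeated observations would increase power even against a tighter non-inferiority boundary". If three GBI measurements had equal pairwise correlation and a constant effect (both assumptions), power at one-sided 0.025 would be 92%, 87% or 82% for correlations of 0.5, 0.7 or 0.9. This softens the practical harm. It does not support the 87%, which is claimed for a single measurement, and section 10.5.2 defines the GBI effectiveness parameter at a single visit.
- **The design is not undermined.** 79% is close to a conventional 80%, the precision argument for 50 patients is unaffected, and section 10.5.3 names tolerance as the primary goal. This stands, and it is why no extra patients are asked for.
- **The loss scenarios have no source.** Also true. Section 10.7 expects few missing data. They are illustrations, and the correction does not depend on them.

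**Conclusion.** The concern holds. At the two-sided 5% level set in section 10.0, the stated design has 79.2% power for non-inferiority on one GBI measurement (80.7% by normal approximation), not 87%. The shortfall is 6 to 8 percentage points, and the type II error is 100 − 79.2 = about 21% rather than 13%. This rests on the plan's own SD of 25, margin of 20, equal true means and 25 evaluable patients per arm, and on reading non-inferiority from the 95% interval for the difference. The defect is an undeclared level in section 10.1 that conflicts with section 10.0.

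**What to change.** In section 10.1, replace the 87% with a statement such as:

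> The power is about 79% to show non-inferiority on a single GBI measurement, defined as the lower limit of the two-sided 95% confidence interval for the difference (Slit Stent II minus BIKA) lying above -20 points, assuming SD 25, true difference 0 and 25 evaluable patients per arm.

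Drop the description of the power as excellent. If the sponsor expects some loss, add the corresponding power and label the loss rate as an assumption (for example, 74% at 22 per arm).

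Declaring a one-sided 5% test as an exception to section 10.0 would also remove the contradiction. But it would relax a rule already stated, whereas restating the power leaves every stated rule in place, so the restatement is preferable.

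The cost is one sentence and a less favourable figure. The sample size of 50, the margin and the two-sided 5% level do not change.

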10.2 Accountability

Accountability by postoperative visit will be calculated as illustrated in Table 10.2-1 below.

Table 10.2-1: Accountability by Postoperative Visit

		Day 0	Day 5-14	Day 30-120
Available for Analysis ²	n/N ¹ (%)			
Missed Visit ³	n/N ¹ (%)			
Discontinued ⁴	n/N ¹ (%)			
Active ⁵	n/N ¹ (%)			
Lost to follow-up ⁶	n/N ¹ (%)			
% Accountability = $\frac{\text{Available for Analysis}}{\text{Enrolled} - \text{Discontinued} - \text{Active}}$				

Where,

- ¹ Enrolled (N) = total number of subject eyes enrolled in the study.
- ² Available for analysis = total number of eyes for whom data are available at each postoperative interval.
- ³ Missed visit = total number of eyes that missed the visit, but were otherwise accounted for. Includes those eyes that missed the visit but were seen at a later visit.
- ⁴ Discontinued = total number of eyes that discontinued follow-up prior to completion of the study for any reason (e.g., device explant, moved away).
- ⁵ Active (not yet eligible for the interval) = total number of eyes that have not yet reached the visit interval.
- ⁶ Lost to follow-up = total number of eyes for whom a visit at the prescribed visit or later was not completed and who are not considered to be active or discontinued.

10.3 Screening

The screening data for all subjects who are screened, but do not meet eligibility criteria, will not be analyzed or tabulated nor collected on the CRFs. The reason for screen failure will be captured on the CRFs.

10.4 Subject Characteristics

The number of subjects included in the safety and/or effectiveness evaluations, subjects completing the study, and the reasons for any withdrawals will be tabulated by counts and percentages. Continuous data will be summarized by mean, standard deviation, and Tukey's five-number summary. Categorical demographic data will be summarized using counts and percentages. Abnormal medical histories, ocular histories, and prior/concurrent medications obtained on the screening visit will be presented in data line listings.

10.5 Outcome Criteria

Complications and adverse events are the primary safety outcomes to be evaluated. All complications and adverse events and their rates of occurrence will be reported. Changes in the subject's symptoms (tearing, irritation) and quality of life as measured by the GBI are the primary effectiveness outcomes.

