4.0 OBJECTIVES

- 1) Assess tolerance of patients to placement of Slit Stent II (Glasgow Benefits Index and Patient Stent Tolerance and Irritation Assessment)
- 2) Assess ocular surface irritation (objective and subjective) following stent placement (Glasgow Benefits Index and Patient Stent Tolerance and Irritation Assessment; Conjunctival and corneal epithelial surface exam and staining under the slit lamp)
- 3) Assess change in quality of life following surgery (Glasgow Benefits Index and Lac-Q Questionnaire)
- 4) Assess change in tearing/epiphora symptoms before and after surgery (Glasgow Benefits Index and Lac-Q Questionnaire)

- 5) Assess change in conjunctival tear lake measurement before and after surgery
- 6) Assess bacterial growth on stents after removal

All criteria will be summarized within the Slit Stent II treatment group. Formal comparisons will be made to no treatment effect and to the standard treatment (control group).

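### Three unranked primary effectiveness outcomes, and the one test the trial is sized for (GBI non-inferiority) is never designated as the deciding test

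*Combined protocol and SAP*

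**What the plan says.** Section 10.5 (Outcome Criteria) says that changes in tearing, irritation and "quality of life as measured by the GBI are the primary effectiveness outcomes". It adds on the safety side that "Complications and adverse events are the primary safety outcomes to be evaluated". The effectiveness outcomes are not ordered.

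Section 4.0 lists six objectives and closes with "Formal comparisons will be made to no treatment effect and to the standard treatment (control group").

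Section 10.0 states that "All testing and confidence intervals will use a two-sided significance level of 5" percent, and that "Specific analyses for the six listed objectives are very similar to one another". It describes summaries and 95% intervals by arm and for the difference, and a mixed model when there are several post-surgery measurements. A separate SAP is still to be written, and "If there are any discrepancies between the statistical analyses described in the SAP versus this protocol, the SAP will prevail". The supplied text gives no date for finalising it.

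Section 10.1 sizes the trial: 25 per arm, GBI standard deviation 25, non-inferiority margin 20 points, 87% power on a single GBI measurement if the true means are equal.

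Section 10.5.2 names the mean GBI composite at the 1-4 month visit as the effectiveness parameter and attaches a 95% t interval for that mean. It gives no between-arm test and no margin. Section 10.5.3 calls patient tolerance the primary goal and functioning like other stents the secondary one. Section 10.5.4 sends other measures, such as slit-lamp findings, to line listings.

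**The concern.** The effectiveness sections give no hierarchy, no rule on whether one or all primary outcomes must succeed, no multiplicity adjustment and no success criterion. The one test with a margin and a power statement stays in the sample-size rationale. A reader of Sections 10.0 to 10.5 could not say which result decides the trial, at which visit, by which estimator or at what alpha.

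Without that, whichever primary outcome looks favourable could be reported as the main finding, and the 5% level attached to it would not be the error rate of the overall claim.

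The comparison with no effect adds a second route. The GBI asks about change since tear duct surgery, and Section 9.3.2 regards DCR as effective. A one-arm GBI mean clearly above zero could therefore reflect the surgery and say nothing about the slits, yet nothing prevents it from being presented as a primary result.

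**Working it through.** **Inputs.** From Section 10.1: n = 25 per arm, SD 25, margin 20, true difference 0, stated power 87%. From Section 10.0: two-sided 5% for every test. From Section 10.5: three primary effectiveness outcomes. Correlations between the outcomes are my assumptions, since the documents give none.

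**Step 1. Reproduce the stated power.** SE = 25 × √(2/25) = 7.07, and margin/SE = 20/7.07 = 2.83.

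- One-sided 5%: Φ(2.83 − 1.645) = 88.2%. The noncentral t with 48 df gives 87.4%, which matches the stated 87%.
- One-sided 2.5%, the equivalent of a two-sided 95% interval: Φ(2.83 − 1.96) = 80.7%, or 79.1% by t. This does not match.

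So the sized test uses a different alpha from the one Section 10.0 sets for all testing.

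**Step 2. Chance of at least one false difference among three tests**, all nulls true and any one result enough for a claim. Under independence it is 1 − (1 − α)³:

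- Either direction: 1 − 0.95³ = 14.3%.
- Favouring the new stent only: 1 − 0.975³ = 7.3%.

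For correlated outcomes I used equicorrelated normal statistics with 400,000 simulated draws:

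| Correlation (assumed) | Favouring new stent | Either direction |
|---|---|---|
| 0 | 7.3% | 14.3% |
| 0.5 | 6.3% | 12.6% |
| 0.9 | 4.2% | 8.3% |
| One test only | 2.5% | 5.0% |

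If all three outcomes had to succeed, the chance of a false overall claim could not exceed the level of a single test, so there would be no inflation.

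**Step 3. Comparison with no effect.** Section 10.1 gives the margin of error for a mean as 0.41 SD. With SD 25 that is 0.41 × 25 = 10.3 points (unrounded multiplier 0.413). A one-arm GBI mean above about 10.3 would exclude zero whatever the other arm shows.

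**Step 4. Power under possible repairs, 25 per arm.**

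- GBI non-inferiority as the single confirmatory test at one-sided 2.5%: 79.1% (t) to 80.7% (normal). Keeping 87% would take 31 (t) or 30 (normal) per arm.
- Bonferroni over three outcomes, one-sided 0.025/3 = 0.0083: GBI power falls to 63.7% (t) or 66.8% (normal). Keeping 87% would take about 39 per arm (normal).
- Requiring all three to succeed: joint power cannot be computed, because no margin or SD is given for tearing or irritation.

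**The case against.** The best defence is that a main test is nearly there. Section 10.5.2 speaks of one effectiveness parameter, the GBI mean at one visit. Section 10.1 sizes the trial on the same scale with a margin, and no other outcome has a margin. The plan is largely one of estimation, with intervals for differences used to show similarity. All of that stands. It means a candidate test exists, so a reader who infers that the plan contains no possible decisive test goes too far. What is missing is the designation.

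The false-difference figures also describe superiority-type findings. When the stents are truly equal, concluding GBI non-inferiority is correct. The relevant null for that test is a 20-point deficit. This is why the favourable-direction figure of about 7% is the better guide and 14% the wider one. Section 10.5 can also be read as naming fewer than three outcomes. With two independent tests the figures are 4.9% and 9.8%.

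Three stronger readings are tempting and not supported:

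- **Much larger inflation.** Eight independent measures would give 1 − 0.95⁸ = 33.7%. That count includes corneal staining, conjunctival staining and tear lake, all slit-lamp items that Section 10.5.4 puts in listings (in tension with Section 4.0), and eye measures in the same patient are unlikely to be independent. Nor should comparisons with no effect be added as false positives, since that null is not expected to hold after DCR for tearing or quality of life.
- **The primary test will be picked after seeing results.** The SAP prevails and carries no date in the supplied text, and the statistician prepares the assignment list. No section describes by-arm outcome review before the SAP is final, and Section 10.7 commits to submitting results whatever the outcome.
- **The error rate is uncontrolled.** The separate SAP may settle it. What can be said is that the protocol does not specify it.

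**Conclusion.** The concern holds as a gap in designation. The plan names three unranked primary effectiveness outcomes and tests at two-sided 5% throughout. It does not carry its one sized test into the analysis sections, and it states a different primary goal in Section 10.5.3.

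The size depends on a rule the documents leave open. If any one of three results suffices, a false difference favouring the new stent has a chance of roughly 6-7% instead of 2.5%, for correlations from 0.5 down to 0, and a false difference in either direction roughly 13-14% instead of 5%. Higher correlation lowers both, and requiring all three removes the inflation. The candidate test also lacks a settled alpha: 87% power holds only at one-sided 5%. This should be corrected before analysis. It does not undermine the design.

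**What to change.** In Sections 10.0 and 10.5:

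1. Designate the between-arm difference in mean GBI composite at the day 30-120 visit, margin 20 points, as the only confirmatory effectiveness test. Judge it by the two-sided 95% confidence interval (one-sided 2.5%), and repeat this in Section 10.5.2 beside the one-group interval. Label the mixed model over all visits as supportive.
2. Report tolerance, irritation, tearing and all other outcomes, including every comparison with no effect, as estimates with 95% intervals and no significance claims. Reconcile Section 10.5.3 with Section 10.5, so that tolerance can remain the main descriptive aim without competing for the confirmatory test.
3. In Section 10.1, state power for this test as about 79% (t) to 81% (normal).
4. Require the SAP to be signed and dated before any outcome is summarised by arm. Qualify the rule that "the SAP will prevail" so that the protocol governs the primary endpoint and margin.

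The cost is a few sentences and no extra patients. The sponsor gives up formal claims on the other outcomes, for which no margin or power is stated, and reports a less favourable power. A Bonferroni split over three outcomes would cost more, leaving GBI power at about 64-67% with 25 per arm.
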